6.3 Control of Bias and Confounding

The following measures for randomization and blinding will be employed to reduce bias:

- All subjects that have undergone implantation during the study period and meet criteria will be recruited to the study
- Measurements and analysis of airway size will be performed in a blinded fashion, without knowledge of subject history

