2.2 Secondary Objectives (if applicable)

- To determine optimal configuration/voltage of the Inspire upper airway stimulator by quantifying changes in upper airway size with multiple implant configurations
- To correlate change in airway size seen on awake endoscopy with outcomes of observed sleep study including AHI and ODI

3 Investigational Plan

Patients who are undergoing Inspire implantation by the principal investigator will be screened to determine whether they meet inclusion criteria and invited to participate in the study. All components of the study will be performed during visits that are scheduled as part of routine postoperative care; these visits will be modified to incorporate study activities. Written consent will be obtained at Visit 1. Subjects will present to clinic (Visit 1) for awake endoscopy during their regularly scheduled postoperative activation appointment. An aerosolized mixture of xylocaine and oxymetolazone (afrin) will be used as a numbing agent prior to awake endoscopy; this is routinely used for awake endoscopic exams in the ENT clinic. The surgeon will perform awake nasal endoscopy while a clinical assistant or nurse activates and configures the device using the Inspire remote control. Device voltage will be titrated to achieve tongue protrusion across the teeth, which is part of the standard method of activation. Endoscopic exam will be recorded and include visualization of baseline airway with device turned off and airway with multiple test configurations and voltages. At the end of this visit, devices will be set to the standard device configuration that is currently used in routine clinical practice (++) . Patients then routinely use their device at home for the following month. The recorded exam will be used by a single blinded member of

CONFIDENTIAL

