the study team to formally measure and analyze airway size in the various conditions after this visit and the “optimal” test configuration will be determined based on airway measurements. Subjects subsequently will undergo an in-lab sleep study for titration of their device (Visit 2). Titration sleep study will ensue with the Inspire device in A) the standard (+++) configuration and B) the “optimal” test configuration. Voltage used with each implant configuration may be increased to achieve effective reduction in AHI at the discretion of the sleep physician; this is routinely performed during titration polysomnography in our current clinical practice. At the end of the sleep study, the device will be returned to the standard setting until further follow up with their sleep medicine physician. This concludes the subject’s participation in the study. Subjects will obtain the results of the sleep study and discuss further device management with their sleep medicine physician during routine follow up.

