3.3 Study Measures

Awake endoscopy will be performed during Visit 1 during which airway size will be video recorded at rest with implant off and with a standardized sequence of implant configurations that were determined by Inspire Corporation during pre-market testing including +++, ---, o-o, -o-, and -+-+. These settings will be tested to determine the voltage at which patients sense tongue movement (sensation threshold) and the voltage at which the tongue is visualized protruding from rest past the teeth (functional threshold). The different electrode configurations will then be tested at various voltages above the subject’s measured functional thresholds.

Measurements of cross-sectional, anterior-to-posterior, and lateral airway size in the retropalatal and retroglossal regions will be taken from recorded endoscopic exams using the image analysis program Amira by Visage Imaging (Richmond, Victoria, Australia). Measurements will take place between Visits 1 and 2. Standard AHI and ODI measurements will take place during in-lab sleep study (Visit 2). Efficacy of awake endoscopy to determine optimal device configuration will be assessed by comparing cross-sectional airway size (retropalatal and retroglossal), AHI and ODI with the standard device configuration compared to airway size, AHI and ODI with the test configuration. In patients for whom the standard configuration (+++) results in greatest airway size, this will be the sole configuration tested during sleep study, and identical values for airway size, AHI, and ODI will be used in analysis comparing the standard configuration with the “test” configuration.

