5.2 Study Intervention

5.2.1 Visit 1: Otolaryngology Clinic for Awake Endoscopy

- Informed consent
- Vital signs: HR, RR, BP, SpO₂, BMI
- Targeted Head and Neck Physical Exam
 - Tongue size, lateral peritonsilar narrowing, palate shape, Modified Mallampati score
- Recorded exam of awake endoscopy at rest and with standardized configurations detailed in section 3.3 (Attachment 1)
 - Measurement and analysis of airway size to be completed by single co-investigator between Visits 1 and 2. Configuration resulting in greatest airway size will be used as test configuration during Visit 2 sleep study.

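### The airway reader's masking is specified only for subject history, not for device configuration and voltage, which is what a within-subject comparison of settings needs

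*Combined protocol and SAP*

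**What the plan says.** Section 3 assigns the readings to one person, in a sentence that runs over a page break: "The recorded exam will be used by a single blinded member of" / "the study team to formally measure and analyze airway size in the various conditions after this visit". It does not say what that person is blinded to. Section 6.3 is the only place that does: "Measurements and analysis of airway size will be performed in a blinded fashion, without knowledge of subject history".

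Section 5.2.1 adds who reads and when: "Measurement and analysis of airway size to be completed by single co-investigator between Visits 1 and 2". The selection rule follows: "Configuration resulting in greatest airway size will be used as test configuration during Visit 2 sleep study".

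Section 3.3 describes the recording as made with the implant off and then "with a standardized sequence of implant configurations that were determined by Inspire Corporation during pre-market testing". It lists five settings, with the standard named first, and adds that they are tested at various voltages above each subject's functional threshold. Where the standard gives the largest airway, "identical values for airway size, AHI, and ODI will be used in analysis comparing the standard configuration with the “test” configuration".

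Section 6.2 uses the same readings in a paired t-test of airway size (largest-airway setting against standard) and in the Pearson correlation with changes in AHI and ODI. No section mentions coded clips, hidden setting labels, a shuffled reading order or a lock on the readings before a code is opened.

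**The concern.** Every airway comparison in this trial is between settings in the same person. Masking to history guards against differences in reading between subjects, which these comparisons already cancel. The knowledge that could bias them is which clip shows the standard configuration and which shows a candidate, and the stated masking does not cover it.

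The readings of one co-investigator serve four purposes: they choose the test configuration, decide who is classed as best on the standard and so contributes a zero difference, supply the airway t-test, and supply one side of the correlation. No second reader is mentioned, so nothing in the plan would reveal a reading tendency.

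**Working it through.** **Plan's own figure.** The plan gives no number on masking or reading error. Its one computed figure, about 30 subjects in section 6.1, does not depend on masking. Reading the stated effect size as d = 0.5 with two-sided alpha 0.05 and power 80%, n = ((1.960 + 0.842)/0.5)² = 31.4, so 32, which agrees with about 30. Nothing below changes it.

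**Step 1: what the stated masking covers.** Write a reading for subject i at setting j as: true size(i, j) + reader effect tied to the subject(i) + reader effect tied to the setting(j) + noise. In the difference between test and standard within subject i, the subject effect cancels whether or not the reader is masked to history. The setting effect does not cancel. Section 6.3 addresses the first and is silent on the second.

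**Step 2: illustration of a setting effect.** All inputs are assumptions, because the documents give no reading SD and no estimate of reader bias: five settings with equal true airway size, independent normal readings with SD 1, and a reader who marks the standard down by b.

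- Share in whom the standard is picked: P(b) = ∫ φ(t + b) Φ(t)⁴ dt
- Apparent gain of the chosen setting: G(b) = b + E[max(Z₁ − b, Z₂, …, Z₅)]

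Simulation with 400,000 replicates gave the following, and numerical integration agrees to the digits shown:

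| b (SD) | Standard picked | Apparent gain (SD) | Excess over b = 0 |
|---|---|---|---|
| 0 | 20% | 1.16 | – |
| 0.25 | 15% | 1.37 | 1.37 − 1.16 = 0.21 |
| 0.5 | 10% | 1.59 | 1.59 − 1.16 = 0.43 |
| 1.0 | 5% | 2.05 | 2.05 − 1.16 = 0.89 |

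The 1.16 SD in the first row comes from choosing the largest of five noisy readings and would remain under perfect masking. Only the last column belongs to this point. With 30 subjects, the number entering with identical values would fall from 30 × 0.20 = 6 to 30 × 0.10 = 3 at b = 0.5. A bias in favour of the standard would move both columns the other way.

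**Step 3: sensitivity to true differences.** Equal true sizes are the most sensitive case. If true sizes vary between settings with SD 2 (reading noise still 1), a bias of 0.5 SD lowers the standard's share from 20% to 15%, not to 10%.

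**Step 4: does it reach AHI, ODI and the correlation?** Further assumptions: the AHI change follows the true airway change plus noise with SD 1.5, and is set to zero where the standard is picked.

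- Equal true sizes: the mean AHI difference and the correlation are both 0.00 for every b from 0 to 1.0.
- True between-setting SD of 1, b from 0 to 1.0: the standardised AHI benefit falls from 0.465 to 0.42, and the correlation weakens from −0.41 to −0.40.

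In these cases a bias against the standard creates no false AHI or correlation signal. It slightly weakens a real one, because it displaces the standard in some subjects where the standard is truly better.

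**The case against.** The strongest reply is that the documents do not show an unmasked reader. Section 3 calls the reader blinded without limit, and the wording in 6.3 need not be exhaustive. That stands. A reader of the plan might infer that the co-investigator sees the setting and can pick out the standard clip, but no section says so. What is shown is that the necessary masking is unspecified.

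It is also tempting to infer that a bias against the standard pushes every result towards the hypothesis. Step 4 does not support this. The reader does not measure AHI or ODI and finishes before the sleep study, so cannot be influenced by its results. The effect that inflates a result directly is on the airway t-test, which is a secondary endpoint.

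The order argument is conditional as well. Section 3.3 lists the standard first but does not say that it is run first. Several voltages per configuration, set from each subject's own threshold, mean that position need not map simply to setting. For the same reason a model with five readings is simpler than the real exam.

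What remains is that the one mask the plan defines cannot protect the comparison the reader makes. If masking to setting was intended, 6.3 should say so.

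**Conclusion.** The point holds as a gap in specified masking that should be closed before any clips are read, because masking cannot be restored afterwards. Its direct effect is on the airway-size comparison: about 0.2, 0.4 or 0.9 SD of added apparent gain for a bias of 0.25, 0.5 or 1.0 SD, with the standard's selection falling from 20% to 15%, 10% or 5%. Those sizes rest on assumed equal settings, independent readings and an assumed bias, none of which the documents supply, and they shrink when settings truly differ. The primary AHI and ODI comparison is affected only through which setting is carried forward and how many zero differences result. The correlation is affected through that choice and through the airway readings themselves. The direction of either effect is not established. The sample size is unaffected.

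**What to change.** In section 6.3, extend the definition so that the reader works unaware of subject history, device configuration, voltage and order of testing. Use the same definition where section 3 calls the reader blinded. Have an existing team member other than the reader cut each recording into clips, give them random codes and shuffle them before they go to the same single reader. Open the code only after that subject's measurements are locked, which fits between Visits 1 and 2.

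The cost is a protocol wording change, a code list and a few minutes of clip handling per subject by someone who is not the reader. It needs no extra reader, visit, procedure or subject. The testing sequence at Visit 1 can stay as it is, since shuffling after recording removes the position cue without changing how the exam is done.

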6.3.1 Baseline Data

Baseline and demographic characteristics will be summarized by standard descriptive statistics (including mean and standard deviation for continuous variables such as age and standard percentages for categorical variables such as gender). Additionally, pertinent information relating to patients’ OSA and history of present illness will be summarized.

6.3.2 Analysis of Primary Outcome of Interest

A paired t-test will be used to compare differences in AHI and ODI using the test configuration compared to the standard device configuration.

7 Safety and Adverse Events

All subjects entered into the study will have detailed information collected on adverse events for the overall study safety analysis.

7.1 Definitions

7.1.1 Adverse Event

An adverse event (AE) is any symptom, sign, illness or experience that develops or worsens in severity during the course of the study. Intercurrent illnesses or injuries should be regarded as adverse events. Abnormal results of diagnostic procedures are considered to be adverse events if the abnormality:

- results in study withdrawal
- is associated with a serious adverse event
- is associated with clinical signs or symptoms

CONFIDENTIAL

- leads to additional treatment or to further diagnostic tests
- is considered by the investigator to be of clinical significance

7.1.2 Serious Adverse Event

Adverse events are classified as serious or non-serious. A serious adverse event is any AE that is:

- fatal
- life-threatening
- requires or prolongs hospital stay
- results in persistent or significant disability or incapacity
- required intervention to prevent permanent impairment or damage
- a congenital anomaly or birth defect
- an important medical event

Important medical events are those that may not be immediately life threatening, but are clearly of major clinical significance. They may jeopardize the subject, and may require intervention to prevent one of the other serious outcomes noted above. For example, drug overdose or abuse, a seizure that did not result in in-patient hospitalization, or intensive treatment of bronchospasm in an emergency department would typically be considered serious.

All adverse events that do not meet any of the criteria for serious should be regarded as non-serious adverse events.

7.2 Recording of Adverse Events

At each contact with the subject, the investigator will seek information on adverse events by specific questioning and, as appropriate, by examination. Information on all adverse events will be recorded immediately in the source document, and also in the appropriate adverse event module of the case report form (CRF). All clearly related signs, symptoms, and abnormal diagnostic procedures results should be recorded in the source document, though should be grouped under one diagnosis.

All adverse events occurring during the study period will be recorded. The clinical course of each event will be followed until resolution, stabilization, or until it has been determined that the study intervention or participation is not the cause. Serious adverse events that are still ongoing at the end of the study period will be followed up to determine the final outcome. Any serious adverse event that occurs after the study period and is considered to be possibly related to the study intervention or study participation will be recorded and reported.

7.3 Relationship of AE to Study

The relationship of each adverse event to the study procedures will be assessed by the PI.

7.4 Reporting of Adverse Events and Unanticipated Problems

The Investigator will promptly notify the Penn IRB of all on-site unanticipated, Adverse Events that are related to the research activity. Other unanticipated problems related to the research involving risk to subjects or others will also be reported promptly. Written reports will be filed using the HS-ERA and in accordance with the Penn IRB timeline of 10 working days.

7.4.1 Follow-up Report

If an AE has not resolved at the time of the initial report and new information arises that changes the investigator's assessment of the event, a follow-up report including all relevant new or reassessed

CONFIDENTIAL

information (e.g., concomitant medication, medical history) should be submitted to the IRB. The investigator is responsible for ensuring that all SAEs are followed until either resolved or stable.

7.4.2 Investigator reporting: notifying the study sponsor

Within six months after completion of study conduct or termination of the applicable study, whichever occurs first, PI will provide Inspire with a written report of the study results. Unless otherwise agreed in writing by the parties, the study report may take the form of a manuscript for publication. The study report will include the study results of the study as a whole. If the study is terminated early, the study report must include, at minimum, the results of the study up until the date of termination.

7.4.3 Data and Safety Monitoring Plan

The study PI will be responsible for monitoring the safety of research subjects throughout the trial.

8 Study Administration, Data Handling and Record Keeping

8.1 Confidentiality

Information about study subjects will be kept confidential and managed according to the requirements of the Health Insurance Portability and Accountability Act of 1996 (HIPAA). Those regulations require a signed subject authorization informing the subject of the following:

- What protected health information (PHI) will be collected from subjects in this study
- Who will have access to that information and why
- Who will use or disclose that information
- The rights of a research subject to revoke their authorization for use of their PHI.

In the event that a subject revokes authorization to collect or use PHI, the investigator, by regulation, retains the ability to use all information collected prior to the revocation of subject authorization. For subjects that have revoked authorization to collect or use PHI, attempts should be made to obtain permission to collect at least vital status (i.e. that the subject is alive) at the end of their scheduled study period.

PHI will be stored on an institutionally secured and managed drive and/or device, accessible only to study personnel.

8.2 Data Collection and Management

Data collected from each phase of the study will be stored on the Otorhinolaryngology – Head and Neck Surgery shared, institutionally secured and managed departmental drive. This drive is only accessible through the UPHS Intranet, has HIPAA compliant security, and is routinely used for other clinical and research purposes of the department. Access will be given only to members of the research team. Data will be stored in encrypted folders and files. Data will be deidentified prior to analyses, and will be made anonymous prior to publication of any studies. Data will be stored for 10 years; this will allow for revisiting data in the event that a full-scale study is performed.

8.3 Records Retention

Records will be retained during the duration of the study and for up to 10 years following conclusion of the study. This is in order to allow for further validation analyses that may be relevant to the disease process.

CONFIDENTIAL

9 Study Monitoring, Auditing, and Inspecting

9.1 Study Monitoring Plan

The study PI will be responsible for ensuring the ongoing quality and integrity of the research study.

9.2 Auditing and Inspecting

The investigator will permit study-related monitoring, audits, and inspections by the EC/IRB, the sponsor, government regulatory bodies, and University compliance and quality assurance groups of all study related documents (e.g. source documents, regulatory documents, data collection instruments, study data etc.). The investigator will ensure the capability for inspections of applicable study-related facilities (e.g. pharmacy, diagnostic laboratory, etc.).

Participation as an investigator in this study implies acceptance of potential inspection by government regulatory authorities and applicable University compliance and quality assurance offices.

10 Ethical Considerations

This study is to be conducted in accordance with applicable US government regulations, standards of Good Clinical Practice, and applicable institutional research policies and procedures. This protocol and any amendments will be submitted to a properly constituted Institutional Review Board (IRB), in agreement with local legal prescriptions, for formal approval of the study conduct. The decision of the IRB concerning the conduct of the study will be made in writing to the investigator and a copy of this decision will be provided to the sponsor before commencement of this study.

10.1 Risks

Overall, this study is designed to pose minimal risk to patients. Flexible laryngoscopy is a standard part of otolaryngology exams, and the associated risks are minor. Risks associated with flexible laryngoscopy include bleeding from the nasal cavity related to passage of the scope, which is typically limited and minor. Extremely rarely patients will have anxiety reaction which results in a sensation of fainting and lightheadedness known as a vasovagal reaction or fainting. There is also the risk of a reaction to the medications in the anesthetic and nasal decongestant spray. Sleep studies are noninvasive and carry minimal risk. Subjects may experience mild skin irritation from electrode adhesive. Risks associated with gathering of medical information include physical, emotional, economic, psychological effects of having information inadvertently discovered in the public domain. This will be mitigated through the use of exclusive HIPAA compliant systems and through deidentification of patient data.

10.2 Benefits

This study has the potential to increase effectiveness of Inspire therapy and to decrease latency from time of implantation to time of effective therapy for the individuals enrolled in the study. If awake endoscopy is deemed a useful adjunctive procedure during implant activation, future patients may also benefit from this new protocol and experience improved sleep outcomes and decreased latency to effective therapy. Improving OSA has the potential to benefit associated comorbidities and overall health for all patients. Decreased latency time to effective therapy has the potential to decrease health system use and costs.

